#### 3.2 Secondary Objectives

- To estimate rates of complete metabolic response on PET/CT imaging obtained 12 weeks after CRT.
- (2) To estimate rates of distant metastasis as the first site of recurrence for patients.
- (3) To estimate the influence of concurrent and consolidative MK-3475 on levels of plasminogen activator inhibitor-1 (PAI-1), a marker of immunosuppressive TGF-B.
- (4) To estimate the influence of concurrent and consolidative MK-3475 on levels of IDO, an enzyme that depletes tryptophan, which is essential for T-cell function.
- (5) To estimate the influence of concurrent and consolidative MK-3475 on levels of MHC class I (CD8+ T cell ligand) and MICA (NK ligand), as measured by MHC.
- (6) To estimate the progression free survival (PFS) in subjects with locally advanced cervical cancer treated with sequential and concurrent administration of pembrolizumab in relation to CRT.
- (7) To estimate the overall survival (OS) in subjects with locally advanced cervical cancer treated with sequential and concurrent administration of pembrolizumab in relation to CRT.

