#### 7.1.3 Efficacy Endpoints

All eligible patients for which a PET/CT imaging is obtained 12 weeks after CRT will be evaluated for complete metabolic response.

All eligible patients with follow-up information on disease status will be evaluated for the occurrence of distant metastasis as the first site of recurrence, progression-free survival and overall survival.

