## 7.2 Sample size and accrual

Results in Jordanova ES, et al 2008, report estimates of CD8+/Treg for normal cervix and cervical cancers tissue for cervical cancer patients who underwent radical hysterectomy with lymphadenectomy.[4] These data provide the assumed "natural baseline" of cancer patients' in this study with CD8+/Tregs being lower in cancer tissue, and results in a Cohen's *d*av effect size (ES) of 0.45. Estimated sample size is based upon being able to detect a similar effect size between CD8+/Tregs at baseline and end of CRT, and baseline to the 12 weeks post CRT assessment without correction for multiple comparisons. Data from Nilges, K et al, 2003, indicates a mean (standard deviation) of 23.32 (15.39) in CD8+/Tregs measured in the tumor infiltrating lymphocytes (TIL) from patients with cervical cancer. Given these data, 44 eligible patients are required (per arm) to assess change in pre/post CD8+/Tregs with an ES of 0.45 with type I and II errors of 10%. Each within arm comparison supports the following hypothesis. Cisplatin can kill T cells, therefore the CRT may eliminate both CD8+ HPV CTL and Tregs, and the ensuing or concurrent pembrolizumab treatment may increase the CD8+/Treg ratio (test that pembrolizumab will increase CD8+/Tregs to an ES of 0.45).

Adjusting for an overall 10% ineligibility/drop-out rate, maximum accrual to the study is estimated at 98 patients. Accrual is estimated at 4 patients a month, thus accrual to the study should be completed by 2.0 years with primary analysis at 3 years.

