#### 7.5 Analyses

The study is designed with sufficient power to assess pre/post change in immune measures with an ES of .45 within each arm and not to detect a predetermined difference in the changes overtime between the two arms. However, data from the study will be used to estimate; the magnitude of the difference in pre/post change for all parameters of interest between the two arms; as well as progression—free and overall survival. With 44 eligible patients per arm we have 67%, 75% and 87% power to detect an ES of 0.45, 0.5 and 0.6, respectively, for continuous immune parameters (normality assumed) with a 10% level t-test. With 44 patients the width of a 90% CI (exact Clopper-Pearson) around the complete metabolic response at 3 months of 70% and the distant metastases rate at 3 years of 20% are (57%, 81%) and (10%, 33%), respectively. Thus, any estimated rate outside of these bounds would be considered promising. For each arm, progression free survival (PFS) and overall survival will be estimated by the product-limit method of Kaplan and Meier along with 90% confidence bands. In patients with complete metabolic response at 3 months, 3-year PFS is 78% (Schwartz et al, 2007). This result will be used to guide interpretation of results on PFS from this study.

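### The 78% three-year PFS reference holds only for complete metabolic responders, yet the only PFS estimates planned are for whole arms, so an arm that merely equals the reference is likely to look worse

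*Combined protocol and SAP*

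**What the plan says.** Secondary objective 6 in section 3.2 is "To estimate the progression free survival (PFS) in subjects with locally advanced cervical cancer treated with sequential and concurrent administration of pembrolizumab", with no restriction by PET response. Section 7.1.3 sets the population for PFS, overall survival and distant metastasis: "All eligible patients with follow-up information on disease status will be evaluated". Section 7.5 gives the method: "For each arm, progression free survival (PFS) and overall survival will be estimated by the product-limit method of Kaplan and Meier", with 90% confidence bands.

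Section 7.5 then supplies its only PFS reference: "In patients with complete metabolic response at 3 months, 3-year PFS is 78" per cent, taken from the cited study of post-therapy PET. The next sentence reads: "This result will be used to guide interpretation of results on PFS from this study". The same paragraph uses 70% as the planning rate for CMR at 3 months, with 44 patients per arm.

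The plan contains no PFS estimate in complete metabolic responders, no landmark at the PET/CT and no PFS reference for an unselected population. The start date of PFS is not defined in section 7.1.3 or 7.5.

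**The concern.** The reference and the estimate describe different populations. Complete metabolic responders are selected after treatment on a favourable result. A patient who progresses or dies before the PET/CT counts as an event in the arm's curve but cannot be in the responder group. If the 78% is laid beside a whole-arm curve, the comparison is biased downward whenever patients without CMR have a 3-year PFS below 78%.

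An external figure carries some weight here. Both arms receive pembrolizumab (section 2.1), and section 1.0 lists historical data as part of the control. With no arm receiving chemoradiation alone, a reader who wants to know whether PFS looks encouraging has only the 78% to turn to.

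**Working it through.** **Inputs from the documents.** Reference 3-year PFS in responders: 78% (section 7.5). CMR rate: 70%, with 90% CI 57% to 81% (section 7.5). Eligible patients per arm: 44 (section 7.2).

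**Input not in the documents.** q, the 3-year PFS of patients without CMR, is shown as an assumed range.

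**Step 1: the plan's own figure.** The exact Clopper-Pearson 90% limits for x of n are the 5% quantile of Beta(x, n − x + 1) and the 95% quantile of Beta(x + 1, n − x). With n = 44 and x = 0.70 × 44 = 30.8, they are 56.7% and 81.2%. This agrees with the stated (57%, 81%). The 78% is external and cannot be reproduced from the documents.

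**Step 2: whole-arm PFS for an arm equal to the reference.** With CMR rate c,

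whole-arm PFS = c × 0.78 + (1 − c) × q.

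At c = 0.70 this is 0.546 + 0.30q. It equals 78% only when q = 78%, that is, when patients without CMR do as well as those with it.

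**Step 3: how often such an arm would look worse.** Take 44 patients with no censoring before 3 years. The exact 90% interval for 29/44 is 52.5% to 77.7%, and for 30/44 it is 54.8% to 79.6%. The upper limit therefore falls below 78% when 29 or fewer patients are progression-free. The point estimate falls below 78% when 34 or fewer are (34/44 = 77.3%, 35/44 = 79.5%). Binomial probabilities at c = 0.70:

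| Assumed q | Whole-arm 3-year PFS | Points below 78% | Chance upper 90% limit < 78% | Chance point estimate < 78% |
|---|---|---|---|---|
| 0 | 54.6% | 23.4 | 95% | 99.9% |
| 20% | 60.6% | 17.4 | 81% | 99% |
| 40% | 66.6% | 11.4 | 52% | 96% |
| 50% | 69.6% | 8.4 | 35% | 90% |
| 60% | 72.6% | 5.4 | 20% | 80% |
| 78% | 78.0% | 0 | 4.5% | 51% |

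The last row shows what a like-for-like comparison would give. Censoring before 3 years would widen the intervals, so these chances of exclusion suit complete 3-year follow-up.

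**Step 4: sensitivity to the CMR rate.** At the ends of the plan's interval, for q from 0 to 50%:

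- c = 0.57: 0.4446 + 0.43q, which is 44.5% to 66.0%.
- c = 0.81: 0.6318 + 0.19q, which is 63.2% to 72.7%.

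Both ranges lie wholly below 78%.

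**The case against.** The strongest reply is that section 7.5 states the responder restriction openly and says only that the figure will guide interpretation. It does not say that the 78% will be set against the whole-arm curve. PET response and disease status are both collected, so an analyst could apply the figure to responders. This is fair as far as it goes: whole-arm use is an inference. It is nevertheless the natural inference, because no other PFS estimate is planned.

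The second reply is that little hangs on it. PFS is the sixth of seven secondary objectives. No test, threshold or go/no-go rule is tied to the 78%, the futility rule in section 7.4.2 is immunologic, and section 4.3.1 calls the clinical endpoints preliminary. That stands, and it limits the consequence to how the result is described.

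A reader might also infer three stronger things that the documents do not support:

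- **That the 78% is counted from the 3-month PET.** The words date the response, not the start of the PFS clock. If the clock did start there, a difference in time origin would be a second problem, but its size cannot be taken from the documents.
- **That an equivalent arm would look clearly worse.** This depends on q. At q = 50% the shortfall is 8 points and the upper limit falls below 78% only 35% of the time.
- **That standard chemoradiation is known not to reach 78% in an unselected arm.** The documents give no unselected 3-year PFS. Their survival anchor, 66% at five years for overall survival (section 4.1), is a different endpoint at a different time.

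**Conclusion.** The point holds as a mismatch between a responder-only reference and whole-arm estimates. The bias is downward for any q below 78%. With the plan's 70% CMR rate and assumed q of 0 to 50%, an arm equal to the reference would be expected to show about 55% to 70%, which is 8 to 23 points short. It is therefore likely to look worse on its point estimate. Whether its 90% interval would exclude 78% is not settled by the documents: the chance is about 81% at q = 20%, 52% at q = 40% and 35% at q = 50%.

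These figures rest on three assumptions: that 70% CMR and 78% PFS in responders can be combined to describe an equivalent arm; that q lies in the range shown; and that all 44 patients are followed for 3 years. The matter affects interpretation of a secondary endpoint only. It is worth correcting, but it does not threaten the primary analyses.

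**What to change.** In section 7.5:

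1. State that 78% is a reference for complete metabolic responders only, and that whole-arm PFS, reported with its 90% confidence bands, is not to be judged against it.
2. Add a Kaplan-Meier PFS estimate in complete metabolic responders, per arm and pooled, landmarked at the PET/CT performed 12 weeks after chemoradiation.
3. Define the study's PFS start date. Confirm from the cited source when its PFS clock starts, and align the responder estimate to that origin before comparing it with 78%. Without this step, the landmark estimate could bring in a time-origin mismatch of its own.

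The cost is some wording and one extra estimate from PET and follow-up data already being collected. The drawback is precision. About 0.70 × 44 ≈ 31 responders are expected per arm, and 24/31 (77%) would have an exact 90% interval of about 62% to 89%. The comparison would be like for like but could only be descriptive.

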### 8.0 LABELING, PACKAGING, STORAGE AND RETURN OF CLINICAL SUPPLIES

#### 8.1 Investigational Product

The investigator shall take responsibility for and shall take all steps to maintain appropriate records and ensure appropriate supply, storage, handling, distribution and usage of investigational product in accordance with the protocol and any applicable laws and regulations.

Clinical Supplies will be provided by Merck as summarized in Table 10.

### Table 10. Product Descriptions

Product Name & Potency	Dosage Form
Pembrolizumab 100 mg/ 4mL	Solution for Injection

## 8.2 Packaging and Labeling Information

Clinical supplies will be affixed with a clinical label in accordance with regulatory requirements.

### 8.3 Clinical Supplies Disclosure

This trial is open-label; therefore, the subject, the trial site personnel, the Sponsor-Investigator and/or designee are not blinded to treatment. Drug identity (name, strength) is included in the label text; random code/disclosure envelopes or lists are not provided.

## 8.4 Storage and Handling Requirements

Clinical supplies must be stored in a secure, limited-access location under the storage conditions specified on the label.

Receipt and dispensing of trial medication must be recorded by an authorized person at the trial site.

Clinical supplies may not be used for any purpose other than that stated in the protocol.

## 8.5 Returns and Reconciliation

The investigator is responsible for keeping accurate records of the clinical supplies received from Merck or designee, the amount dispensed to and returned by the subjects and the amount remaining at the conclusion of the trial.

Upon completion or termination of the study, all unused and/or partially used investigational product will be destroyed at the site per institutional policy. It is the Investigator's responsibility to arrange for disposal of all empty containers, provided that procedures for proper disposal have been established according to applicable federal, state, local and institutional guidelines and procedures, and provided that appropriate records of disposal are kept.

### 9.0 ADMINISTRATIVE AND REGULATORY DETAILS

#### 9.1 Institutional Review Board (IRB) Approval and Consent

It is expected that the IRB will have the proper representation and function in accordance with federally mandated regulations. The IRB should approve the consent form and protocol.

In obtaining and documenting informed consent, the investigator should comply with the applicable regulatory requirement(s), and should adhere to all ICH E6 principles and Good Clinical Practice (GCP), to ethical principles that have their origin in the Declaration of Helsinki.

Before recruitment and enrollment onto this study, the subject will be given a full explanation of the study and will be given the opportunity to review the consent form. Each consent form must include all the relevant elements currently required by the FDA Regulations and local or state regulations. Once this essential information has been provided to the subject and the investigator is assured that the subject understands the implications of participating in the study, the subject will be asked to give consent to participate in the study by signing an IRB-approved consent form.

Prior to a subject's participation in the trial, the written informed consent form should be signed and personally dated by the subject and by the person who conducted the informed consent discussion.

### 9.2 Adherence to the Protocol

Except for an emergency situation in which proper care for the protection, safety, and well-being of the study subject requires alternative treatment, the study shall be conducted exactly as described in the approved protocol. The Institutional Review Board will approve all aspects of this study, including the clinical trial protocol, informed consent documents, and patient materials. Modifications to the protocol or consent form will be reviewed and approved by the IRB prior to implementation, except when necessary to eliminate apparent immediate hazards to the study participants. The study will undergo continuing IRB review based on the level of risk as assessed by the IRB. This review will take place no less than annually. Participating sites will be responsible for ensuring their consent forms are written in accord with 21 CFR 50.

## 9.2.1 Emergency Modifications

Investigators may implement a deviation from, or a change of, the protocol to eliminate an immediate hazard(s) to trial subjects without prior IRB approval/favorable opinion.

For any such emergency modification implemented, a UVA IRB modification form must be completed by study Personnel within five (5) business days of making the change.

#### 9.2.2 Other Protocol Deviations/Violations

**Protocol Deviations:** A protocol deviation is any unplanned variance from an IRB approved protocol that:

- Is generally noted or recognized after it occurs
- Has no substantive effect on the risks to research participants

#### Protocol/Amendment No.: UVA-LACC-PD201, Version 4.0, 06 March 2018

- Has no substantive effect on the scientific integrity of the research plan or the value of the data collected
- Did not result from willful or knowing misconduct on the part of the investigator(s).

Study personnel will record the deviation, and report to any Sponsor-Investigator or data and safety monitoring committee in accordance with their policies. Deviations should be summarized and reported to the IRB at the time of continuing review.

Protocol Violations: An unplanned protocol variance is considered a violation if the variance:

- Has harmed or increased the risk of harm to one or more research participants.
- Has damaged the scientific integrity of the data collected for the study.
- Results from willful or knowing misconduct on the part of the investigator(s).
- Demonstrates serious or continuing noncompliance with federal regulations, State laws, or University policies.

Violations should be reported by study personnel to the IRB within one (1) week of the investigator becoming aware of the event.

## 9.3 Record Retention

Study documentation includes all Case Report Forms, data correction forms or queries, source documents, Sponsor-Investigator correspondence, monitoring logs/letters, and regulatory documents (e.g., protocol and amendments, IRB correspondence and approval, signed subject consent forms).

Source documents include all recordings of observations or notations of clinical activities and all reports and records necessary for the evaluation and reconstruction of the clinical research study.

Government agency regulations and directives require that all study documentation pertaining to the conduct of a clinical trial must be retained by the study investigator. In the case of a study with a drug seeking regulatory approval and marketing, these documents shall be retained for at least two years after the last approval of marketing application in an International Conference on Harmonization (ICH) region. In all other cases, study documents should be kept on file until three years after the completion and final study report of this investigational study.

## 9.4 Obligations of Investigators

The Principal Investigator is responsible for the conduct of the clinical trial at the site in accordance with Title 21 of the Code of Federal Regulations, all applicable local regulatory laws and regulations and/or the Declaration of Helsinki. The Principal Investigator is responsible for personally overseeing the treatment of all study subjects. The Principal Investigator must assure that all study site personnel, including sub-investigators and other study staff members, adhere to the study protocol and all FDA/GCP/NCI regulations and guidelines regarding clinical trials both during and after study completion. It is the responsibility of the Principal Investigator to ensure that all study site personnel are aware that the study protocol and all data generated is confidential and should not be disclosed to third parties (with the exception of local and national regulatory bodies which require access for oversight purposes).

Protocol/Amendment No.: UVA-LACC-PD201, Version 4.0, 06 March 2018

The Principal Investigator at each institution or site will be responsible for assuring that all the required data will be collected and entered onto the Case Report Forms. Periodically, monitoring visits will be conducted and the Principal Investigator will provide access to his/her original records to permit verification of proper entry of data. At the completion of the study, all case report forms will be reviewed by the Principal Investigator and will require his/her final signature to verify the accuracy of the data.

## 9.5 Compliance with Trial Registration and Results Posting Requirements

Under the terms of the Food and Drug Administration Modernization Act (FDAMA) and the Food and Drug Administration Amendments Act (FDAAA), the Sponsor of the trial is solely responsible for determining whether the trial and its results are subject to the requirements for submission to the Clinical Trials Data Bank, http://www.clinicaltrials.gov. Information posted will allow subjects to identify potentially appropriate trials for their disease conditions and pursue participation by calling a central contact number for further information on appropriate trial locations and trial site contact information.

### **11.0 APPENDICES**

## 11.1 ECOG Performance Status

Grade	Description
0	Normal activity. Fully active, able to carry on all pre-disease performance without restriction.
1	Symptoms, but ambulatory. Restricted in physically strenuous activity, but ambulatory and able to carry out work of a light or sedentary nature (e.g., light housework, office work).
2	In bed <50% of the time. Ambulatory and capable of all self-care, but unable to carry out any work activities. Up and about more than 50% of waking hours.
3	In bed >50% of the time. Capable of only limited self-care, confined to bed or chair more than 50% of waking hours.
4	100% bedridden. Completely disabled. Cannot carry on any self-care. Totally confined to bed or chair.
5	Dead.
* As published in Am. J. Clin. Oncol.: Oken, M.M., Creech, R.H., Tormey, D.C., Horton, J., Davis, T.E., McFadden, E.T., Carbone, P.P.: Toxicity And Response Criteria Of The Eastern Cooperative Oncology Group. Am J Clin Oncol 5:649-655, 1982. The Eastern Cooperative Oncology Group, Robert Comis M.D., Group Chair.	

## 11.2 Common Terminology Criteria for Adverse Events V4.0 (CTCAE)

The descriptions and grading scales found in the revised NCI Common Terminology Criteria for Adverse Events (CTCAE) version 4.03 will be utilized for adverse event reporting. (http://ctep.cancer.gov/reporting/ctc.html)
